6.2 Toxicity Management

The management of specific AEs and laboratory parameters is described below and in the **Operations Manual**. This includes the following laboratory abnormalities:

If a subject experiences a post-baseline increase in ALT to $> 5 \times$ ULN which is also $> 2 \times$ baseline value, the subject should have a confirmatory ALT measurement performed.

If, the ALT increase is confirmed to be $> 5 \times$ ULN which is also $> 2 \times$ baseline value, the recommendations below should be followed:

- Complete hepatic questionnaire.
- Evaluate for alternate etiology of ALT elevation; document in the source, update the medical history and concomitant medications eCRF (if applicable), and obtain Anti-hepatitis A virus immunoglobulin M (HAV IgM), Anti-hepatitis A virus total (HAV Total), Anti-HBc IgM, Anti-HBc Total, Anti-HBs, HBV DNA, HBsAg, Anti-hepatitis E virus immunoglobulin M (HEV IgM), Anti-hepatitis E virus immunoglobulin G (HEV IgG) and HEV RNA, and other additional tests, as appropriate.
- Manage the subject as medically appropriate.
- Repeat ALT, AST, total and fractionated bilirubin, alkaline phosphatase and international normalized ratio (INR) within 1 week. Repeat liver chemistries as indicated until resolution.

Discontinue study drug if any of the following is observed at any time:

- ALT level is $\geq 20 \times$ ULN in the absence of an alternate etiology.
- Increasing direct bilirubin or INR or onset of symptoms/signs of hepatitis.
- At the discretion of the investigator.

Alternate management of ALT increases is permitted with approval of the AbbVie Therapeutic Area Medical Director.

6.3 Product Complaint

A Product Complaint is any complaint related to the biologic or drug component of the product.

For a product this may include, but is not limited to, damaged/broken product or packaging, product appearance whose color/markings do not match the labeling, labeling discrepancies/inadequacies in the labeling/instructions (example: printing illegible), missing components/product, or packaging issues.

Product Complaints concerning the investigational product must be reported to AbbVie within 24 hours of the study site's knowledge of the event. Product Complaints occurring during the study will be followed up to a satisfactory conclusion.

7 STATISTICAL METHODS & DETERMINATION OF SAMPLE SIZE

7.1 Statistical and Analytical Plans

Complete and specific details of the statistical analysis will be described and fully documented in the Statistical Analysis Plan (SAP). The SAP will be finalized prior to the database lock. The statistical analyses will be performed using a statistical analysis system (SAS) (SAS Institute Inc., Cary, NC, USA).

7.2 Definition for Analysis Populations

The Intention-to-Treat (ITT) population includes all enrolled subjects who received at least 1 dose of study drug. The ITT population will be used for all secondary and exploratory efficacy analyses as well as for baseline analyses.

The mITT population includes all enrolled subjects who received at least 1 dose of study drug, excluding subjects who did not achieve SVR₁₂ for reasons other than virologic failure. The mITT population will be used for the primary efficacy analysis.

The Safety Analysis Set consists of all subjects who received at least 1 dose of study drug.

7.3 Statistical Analyses

Primary Analysis

The primary efficacy endpoint is the percentage of subjects who achieve SVR₁₂ (HCV RNA < LLOQ 12 weeks after the last actual dose of study drug) across genotypes in adults with HCV GT1 – GT6. The primary endpoint will be analyzed based on mITT population.

The secondary efficacy endpoints of SVR₁₂, on-treatment virologic failure, and post-treatment relapse will be analyzed across genotypes in adults with HCV GT1 – GT6 based on ITT population.

For the analysis of post-treatment HCV virologic relapse, completion of treatment is defined as any subject with study drug duration of 52 days or greater.

The number and percentage of subjects achieving SVR₁₂ will be summarized along with a two-sided 95% confidence interval using the normal approximation to the binomial distribution, unless the number of subjects who fail to achieve SVR₁₂ is less than 5, where the Wilson's score method will be used for the confidence interval instead. A summary of reason for SVR₁₂ non-response (e.g., on-treatment virologic failure, relapse, other) will be provided.

The efficacy of 8-week treatment duration for subjects with APRI ≤ 1 based on mITT population will be established if the lower boundary of two-sided 95% confidence interval for the percentage of subjects achieving SVR₁₂ is greater than 92.4% among HCV GT1 – GT6 subjects.

The efficacy of 8-week treatment duration for subjects with $APRI \leq 1$ based on ITT population will be established if the lower boundary of two-sided 95% confidence interval for the percentage of subjects achieving SVR_{12} is greater than 91.4% among HCV GT1- GT6 subjects.

In order to control the Type I error rate, a fixed sequence testing procedure will be used for the SVR_{12} endpoints. Only if success has been demonstrated for the primary endpoint of SVR_{12} based on mITT population, will the testing proceed to the first secondary endpoint of SVR_{12} based on ITT population.

The multiplicity controlled efficacy endpoints will be tested sequentially in the following order:

1. Efficacy of the 8-week treatment duration based on mITT population: If this endpoint is statistically significant, then proceed to the following efficacy endpoint. If this endpoint is not statistically significant then stop the testing procedure and declare that no endpoints in the study met statistical significance.
2. Efficacy of the 8-week treatment duration based on ITT population: If this endpoint is statistically significant, then declare the SVR_{12} endpoint is statistically significant for both mITT and ITT populations. If not, then announce that SVR_{12} endpoint is statistically significant only for mITT population.

For on-treatment virologic failure and post-treatment relapse, the number and percentage of subjects will be summarized along with a two-sided 95% confidence interval using Wilson's score method.

Further details on the primary and other efficacy analyses are provided in the SAP.

Sample Size Estimation

It is planned to enroll approximately 230 adult subjects with chronic HCV GT1 – GT6 infection with $APRI \leq 1$ who are HCV treatment-naïve in the study. The enrollment will be monitored to have approximately maximum 46 GT3-infected subjects (20% of total subjects).

With approximately 230 GT1 – GT6 infected subjects (with 46 GT3 subjects) in mITT analysis, this study has approximately 90% power to demonstrate efficacy of the 8-week treatment in terms of SVR_{12} rate (i.e., a two-sided 95% lower confidence bound above 92.4%), assuming that 98% of the GT1, GT2, GT4, GT5, and GT6-infected subjects with $APRI \leq 1$ and 94% of the GT3-infected subjects with $APRI \leq 1$ achieve SVR_{12} .

With 230 GT1 – GT6 infected subjects (with 46 GT3 subjects) in ITT analysis, this study has approximately 83% power to demonstrate efficacy of the 8-week treatment in terms of SVR_{12} rate (i.e., a two-sided 95% lower confidence bound above 91.4%), assuming that 97% of the GT1, GT2, GT4, GT5, and GT6-infected subjects with $APRI \leq 1$ and 93% of the GT3-infected subjects with $APRI \leq 1$ achieve SVR_{12} .

Efficacy for the 8-week regimen in this study is established by demonstrating similarity to the historical control regimen of GLE/PIB administered for 8 weeks in treatment-naïve subjects without cirrhosis. The SVR_{12} rate of the historical control regimen is calculated, and a threshold is determined by subtracting a non-inferiority margin of 6% from the historical SVR_{12} rate. Efficacy is established if the lower 95% confidence boundary of the SVR_{12} rate in the 8-week regimen is greater than the threshold. Efficacy for the 8-week regimen in this study is established by demonstrating the lower boundary of 95% CI for SVR_{12} rate is higher than a cut off value (92.4% and 91.4% for mITT and ITT population, respectively).

In the registrational studies, different SVR₁₂ rates based on mITT population have been observed among GT3- and non-GT3-infected treatment-naïve subjects without cirrhosis assigned to 8 weeks of GLE/PIB treatment. In these studies, approximately 98.9% and 96.2% SVR₁₂ has been observed among non-cirrhotic, treatment naïve chronic HCV GT1, GT2, GT4, GT5, and GT6-infected subjects and GT3 subjects, respectively.¹¹⁻¹³ Hence, for the non-cirrhotic GT1 – GT6-infected subjects, based on mITT population, the historical SVR₁₂ rate of 98.4% is estimated based on a weighted average of 80% GT1, GT2, GT4, GT5, and GT6 historical rate and 20% GT3 historical rate. To establish cut off for efficacy based on mITT population, a margin of 6% is applied to the historical control rate of 98.4%, resulting in a threshold of 92.4%.

Historical SVR₁₂ rate based on ITT population depends on the non-virologic failure in a study. Study-to-study variability has been observed in non-virologic failure rates, and is typically around 1%. The observed rate of non-virologic failure in the registrational program is 1.2% (29/2369).¹¹⁻¹³ For this reason, this study assumes that the historical SVR₁₂ rate based on ITT population for treatment naïve non-cirrhotic subjects is 97.4% (with 1% non virologic failure). To establish cut off for efficacy based on ITT population, a margin of 6% is applied to the historical control rate of 97.4%, resulting in a threshold of 91.4%.

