4.4 Sample Size Justification

It is planned to enroll approximately 230 adult subjects with chronic HCV GT1 – GT6 infection with APRI ≤ 1 who are HCV treatment-naïve in the study. The enrollment will be monitored to have approximately maximum 46 GT3-infected subjects (20% of total subjects).

With approximately 230 GT1 – GT6 infected subjects (including 46 GT3 subjects) in mITT analysis, this study has approximately 90% power to demonstrate efficacy of the 8-week treatment in terms of SVR₁₂ rate (i.e., a two-sided 95% lower confidence bound above 92.4%), assuming that 98% of the GT1, GT2, GT4, GT5, and GT6-infected subjects with APRI ≤ 1 and 94% of the GT3-infected subjects with APRI ≤ 1 achieve SVR₁₂.

With 230 GT1 – GT6 infected subjects (including 46 GT3 subjects) in ITT analysis, this study has approximately 83% power to demonstrate efficacy of the 8-week treatment in terms of SVR₁₂ rate (i.e., a two-sided 95% lower confidence bound above 91.4%), assuming that 97% of the GT1, GT2, GT4, GT5, and GT6-infected subjects with APRI ≤ 1 and 93% of the GT3-infected subjects with APRI ≤ 1 achieve SVR₁₂.

Efficacy for the 8-week regimen in this study is established by demonstrating similarity to the historical control regimen of GLE/PIB administered for 8 weeks in treatment naïve non cirrhotic patients. The SVR₁₂ rate of the historical control regimen is calculated, and a threshold is determined by subtracting a non-inferiority margin of 6% from the historical SVR₁₂ rate. Efficacy is established if the lower 95% confidence boundary of the SVR₁₂ rate in the 8-week regimen is greater than the threshold. Efficacy for the 8-week regimen

in this study is established by demonstrating the lower boundary of 95% CI for SVR₁₂ rate is higher than a cut off value (92.4% and 91.4% for mITT and ITT population, respectively).

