6.2 Primary Efficacy Analysis

The primary efficacy endpoint is SVR₁₂ (HCV RNA < LLOQ 12 weeks after the last actual dose of study drug). The number and percentage of subjects in the mITT population achieving SVR₁₂ will be summarized and a two-sided 95% confidence interval will be calculated using the normal approximation to the binomial distribution. If the number of SVR₁₂ non-responders is less than five, then the Wilson's score method will be used to calculate the confidence interval. As a sensitivity analysis, Wilson's score method will be used to calculate the confidence interval if the number of SVR₁₂ non-responders is greater than or equal to five.

The efficacy of 8-week treatment duration for HCV GT1 – GT6 subjects with APRI ≤ 1 based on mITT population will be established if the lower boundary of two-sided 95% confidence interval for the percentage of subjects achieving SVR₁₂ is greater than 92.4%.

A summary of reasons for SVR₁₂ non-response (e.g., on-treatment virologic failure, relapse) in the mITT population will be provided. A listing of subjects who do not

achieve SVR₁₂ by reason for non-response will also be provided. A listing of subjects excluded from the mITT population will be provided.

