6.4 Other Efficacy Analyses

The following additional efficacy endpoints will be summarized and analyzed for the ITT population:

- The percentage of subjects with HCV RNA < LLOQ at each post-baseline visit in the Treatment Period (using data as observed);
- The percentage of subjects with SVR₄;
- Adherence to treatment;
- The percentage of subjects in the ITT population with virologic failure by baseline FibroTest score (≤ 0.75 or > 0.75);
- The percentage of subjects in the ITT population with on-treatment virologic failure by HCV genotype;

- The percentage of subjects in the ITT population with post-treatment relapse by HCV genotype.

In the above analyses, the percentage of subjects with a two-sided 95% Wilson score interval will be summarized. Imputations for missing data will be performed as described in Section 4.7 for SVR, where a missing response will be imputed as a failure after performing the described imputation. All other endpoints will be presented using data as observed.

A summary of the subjects who completed treatment and relapsed will be prepared displaying the number of subjects relapsing overall and by SVR visit window (within the SVR₄ window or within the SVR₁₂ window), including the subject number and the SVR visit window corresponding to the first occurrence of relapse. A similar listing will be prepared for subjects who prematurely discontinued treatment and relapsed after having HCV RNA < LLOQ at their Final Treatment Visit.

Descriptive statistics (mean, standard deviation, median, minimum, and maximum; number and percentage) will be presented for exposure during the treatment period. Compliance (adherence) will be calculated for each subject and summarized with the mean, median, standard deviation, minimum, and maximum for each treatment arm and overall. A listing of compliance for each subject will be provided. The percentage of compliant subjects will be summarized based on data as observed. An additional summary of the percentage of compliant subjects will be provided where subjects who are missing study drug accountability records will be imputed as non-compliant.

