6.5 Efficacy Subgroup Analyses

The number and percentage of subjects with SVR₁₂ in the ITT and mITT populations will be presented for the following key subgroups:

- Baseline APRI (≤ 0.7 or > 0.7) and (≤ 0.5 or > 0.5);
- HCV genotype (1, 2, 3, 4, 5, or 6) and available subtype;
- Age (< 65 or ≥ 65 years) and (< 75 or ≥ 75 years);
- Baseline FibroTest score (≤ 0.75 or > 0.75);
- Adherence to treatment (yes/no).

The two-sided 95% Wilson score confidence interval will be produced if there are at least 10 subjects in the subgroup.

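### Both SVR12 success rules are decided on a normal-approximation lower limit whose exact one-sided error is 3.6% to 6.4%, against an implied 2.5%, and which does not fit the stated power

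*Protocol*

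**What the plan says.** Protocol 7.3 (Statistical Analyses) summarises SVR12 with a "two-sided 95% confidence interval using the normal approximation to the binomial distribution, unless the number of subjects who fail to achieve" SVR12 is under five, in which case Wilson's score method is used. Efficacy is established if the lower limit exceeds 92.4% in the mITT population and then, in fixed sequence, 91.4% in the ITT population.

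SAP 6.2 says the same for the primary test: "a two-sided 95% confidence interval will be calculated using the normal approximation to the binomial distribution". SAP 6.3 follows suit for ITT. With five or more non-responders, Wilson has only a supporting role: "As a sensitivity analysis, Wilson's score method will be used to calculate the confidence interval".

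On power at 230 subjects, Protocol 7.3 says for mITT that "this study has approximately 90% power to demonstrate efficacy of the 8-week treatment", and SAP 4.4 says for ITT that "this study has approximately 83% power to demonstrate efficacy of the 8-week treatment". Neither document names the test or formula behind these figures.

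Elsewhere the plan uses Wilson at any count. For on-treatment failure and relapse, Protocol 7.3 has results "summarized along with a two-sided 95% confidence interval using Wilson's score method". For the other efficacy endpoints, including SVR4, SAP 6.4 says "the percentage of subjects with a two-sided 95% Wilson score interval will be summarized". For the SVR12 subgroups, SAP 6.5 says "The two-sided 95% Wilson score confidence interval will be produced if there are at least 10 subjects in the subgroup".

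**The concern.** The normal-approximation (Wald) interval estimates its standard error from the observed proportion. When that proportion is near 1 the standard error is too small and the lower limit too high, so a rule based on it passes too often. The switch to Wilson below five failures looks like a safeguard for this situation, but it acts far from the counts at which the trial passes or fails.

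The primary claim of a single-arm trial with no concurrent control rests on this limit, after a 6-point margin has already been allowed. The fixed sequence in Protocol 7.3 and SAP 4.6 is there to control Type I error, but it deals only with multiplicity. It cannot hold a level that the test at each step does not hold. There is also a visible practical risk: the primary analysis could declare success while the SAP's own sensitivity interval falls below the threshold.

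**Working it through.** **Inputs.** N = 230, of which 46 GT3 and 184 non-GT3; thresholds 92.4% and 91.4%; assumed SVR12 98%/94% (mITT) and 97%/93% (ITT) for non-GT3/GT3 (Protocol 7.3, SAP 4.4). The mixtures are 0.8×98 + 0.2×94 = 97.2% and 0.8×97 + 0.2×93 = 96.2%. Non-virologic failure is about 1% (Protocol 7.3). No numeric alpha is written; a two-sided 95% limit implies 2.5% one-sided. The range N = 215 to 240 is my assumption around the planned 230.

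**Step 1: reproduce the stated power.**

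Score test with null variance: Φ{[(p − p0)√N − 1.96√(p0(1 − p0))] / √(p(1 − p))}.
- mITT: (0.048×15.166 − 1.96×0.2650)/0.1650 = 1.264, so 89.7%.
- ITT: (0.048×15.166 − 1.96×0.2804)/0.1912 = 0.933, so 82.5%.

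Wald formula: Φ{(p − p0)√N/√(p(1 − p)) − 1.96} gives 99.3% and 96.8%. The stated figures of about 90% and 83% therefore fit a score-type calculation and not a Wald one.

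**Step 2: lower limits at N = 230.** With p̂ the observed SVR12 proportion:
- Wald: p̂ − 1.96√(p̂(1 − p̂)/N)
- Wilson: [p̂ + z²/2N − z√(p̂(1 − p̂)/N + z²/4N²)] / (1 + z²/N), with z = 1.96

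For 11 failures, p̂ = 219/230 = 0.9522. Wald gives 0.9522 − 1.96×0.01407 = 92.46%; Wilson gives (0.9522 + 0.0084 − 0.0288)/1.0167 = 91.64%.

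| Failures of 230 | Wald | Wilson |
|---|---|---|
| 9 | 93.58% | 92.73% |
| 10 | 93.02% | 92.18% |
| 11 | 92.46% | 91.64% |
| 12 | 91.91% | 91.10% |

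Against 92.4% (mITT) the planned rule passes at 11 or fewer failures and Wilson at 9 or fewer. Against 91.4% (ITT) the pass marks are 12 and 11. The two intervals disagree at 10 or 11 mITT failures and at 12 ITT failures.

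**Step 3: exact error and power.** Error = P(X ≤ c), with X ~ Binomial(N, 7.6%) for mITT or Binomial(N, 8.6%) for ITT, and c the pass mark. Power is the exact convolution of the 184 non-GT3 and 46 GT3 subjects.

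| N = 230 | Pass mark | Exact error | Power |
|---|---|---|---|
| mITT, planned rule | ≤11 | 6.16% | 97.1% |
| mITT, Wilson | ≤9 | 1.69% | 88.7% |
| ITT, planned rule | ≤12 | 3.67% | 89.9% |
| ITT, Wilson | ≤11 | 1.95% | 83.2% |

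**Step 4: other sample sizes.** The error moves in a sawtooth with N. Over N = 215 to 240 the planned rule exceeds 2.5% at all 26 sizes:
- mITT: 3.65% (N = 228, pass mark 10) to 6.38% (N = 229, pass mark 11), mean 5.0%, at or above 5% at 12 sizes.
- ITT: 3.60% to 6.14%.

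Across this range the planned pass marks lie between 10 and 13 failures, so the switch below five failures never alters a decision.

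**Step 5: average over the mITT size.** The mITT population drops non-virologic failures, so its N is random. With 230 dosed and non-virologic failure rate r, the error is Σk Binomial(k; 230, r) × error at N = 230 − k.

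| r | Planned rule | Wilson |
|---|---|---|
| 0.5% | 5.46% | 1.78% |
| 1% | 4.63% | 1.87% |
| 1.2% | 4.44% | 1.91% |
| 2% | 4.20% | 2.05% |
| 3% | 4.44% | 2.15% |

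**Step 6: chance that the two intervals disagree.** Under the plan's assumed rates: mITT 8.4% at N = 230 and 5.2% at N = 228 (182 + 46); ITT 6.7% at N = 230. At the historical mITT rates of 98.9% and 96.2% it is about 0.4%.

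**The case against.** The rule is pre-specified, and the two documents agree on it. SAP 6.2 and 6.3 already require Wilson alongside at five or more failures, so a borderline result would be shown both ways, and it is clear which interval decides. Under the planned rule the power is higher than stated, so the trial is not underpowered. At N = 228, nearer to what 1% non-virologic failure implies, the mITT error is 3.65% and only one count (10 failures) is in dispute. The N = 230 mITT rule has a 2.5% error at a true rate of about 91.6%, the N = 228 rule at about 92.1% and the N = 230 ITT rule at about 91.1%. That is a slippage of roughly 0.3 to 0.8 points against a 6-point margin that is itself a judgement. The ITT errors are stand-alone; because ITT is tested only after mITT succeeds, the chance of reaching and falsely passing it cannot be higher. Wilson itself goes slightly over 2.5% at a few sizes.

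All of this is true and it limits the practical size. It does not rescue the rule. Pre-specification and disclosure do not correct an inflated error, and 3.65% is the lowest mITT error in the range checked. Although it is clear that Wilson does not decide, nothing says how a conflict between the two intervals should be interpreted. Wilson's excess is at most 0.07 points, at two of 26 sizes per test; the planned rule's excess is at least 1.1 points at every size. The difference between 90% and 89% mITT power is small; the point is that the sample size fits a stricter test than the one that decides.

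**Conclusion.** The concern holds and should be fixed before database lock. The rule that decides both SVR12 claims has an exact one-sided error of 3.65% to 6.38% (mITT) and 3.60% to 6.14% (ITT) over N = 215 to 240. At the plan's own 1% non-virologic failure rate the averaged mITT error is 4.6%, nearly twice the implied 2.5%. The stated power belongs to a score-type or exact test, and the planned rule is more lenient than that.

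This rests on reading the two-sided 95% limit as a 2.5% one-sided level, on a common binomial rate at the threshold, and on the assumed range of N. Letting GT3 be 2.7 or 4 points below the other genotypes at the same average leaves the N = 230 errors at about 6.1% and 3.6% to 3.7%. If true SVR12 is near the historical rates, the choice of interval will rarely matter; it matters when the result is close to the threshold.

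**What to change.** In Protocol 7.3 and SAP 6.2 and 6.3, make Wilson's score interval the deciding interval for both SVR12 tests at every failure count. Delete the switch at five failures and report the normal-approximation interval as supportive only. In Protocol 7.3 and SAP 4.4, name the test behind the power figures and restate mITT power as about 89%; the ITT figure of 83% stands.

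The change needs no extra subjects or data, since both intervals are already in the SAP. It does alter the primary decision rule, so it needs a protocol amendment with the ethics review that Protocol 8.1 requires. At N = 230 the pass mark tightens from 11 to 9 failures (mITT) and from 12 to 11 (ITT). Power moves from 97.1% and 89.9% to 88.7% and 83.2%, close to what the plan already states; at N = 228 mITT power moves from 94.2% to 89.0%. Wilson's error stays at or below 2.57% over N = 215 to 240, slightly above 2.5% only at N = 220 and 237 (mITT) and 224 and 239 (ITT). If strict control is wanted, the Clopper-Pearson interval gives the same pass marks at N = 230 and does not exceed 2.5% anywhere in that range (maximum 2.47% mITT, 2.44% ITT).

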
Objective(s) and Endpoint(s):	
The primary objective of this study is:
 
 To demonstrate the efficacy (by achieving high sustained virologic response 12 weeks post dosing [SVR₁₂] rate) and safety of 8 weeks of treatment with the GLE/PIB combination regimen in treatment naïve adults with HCV GT 1 – GT6 infection with APRI ≤ 1. The primary efficacy objective will be assessed based on modified intention-to-treat (mITT) population across genotypes HCV GT1 – GT6. 
The primary efficacy endpoint is the percentage of subjects who achieve SVR₁₂ (HCV RNA < lower limit of quantification [LLOQ] 12 weeks after the last actual dose of study drug) across genotypes in adults with HCV GT1 – GT6 based on mITT population.

Investigator(s):	
Multicenter

Study Site(s):	
Approximately 43 sites worldwide.

Study Population and Number of Subjects to be Enrolled:	
Approximately 230 subjects with chronic HCV GT1 – 6 (maximum of 20% [46] enrollment of GT3 subjects) and APRI ≤ 1, who meet all eligibility criteria.

Investigational Plan:	
Non-randomised, open label, Phase 3b study.

Key Eligibility Criteria:	
Demographic and Laboratory Assessments
 
 ✔ Adult male or female, at least 18 years old at the time of screening. ✔ Laboratory values meeting the following criteria within the Screening period prior to the first dose of study drug: 
 • Platelets ≥ 150,000 cells/mm³ • Alanine aminotransferase (ALT) ≤ 10 × upper limit of normal (ULN) • Aspartate aminotransferase (AST) ≤ 10 × ULN • Direct bilirubin ≤ ULN • Albumin ≥ lower limit of normal (LLN) • Calculated creatinine clearance (using Cockcroft-Gault method) ≥ 30 mL/min • A negative hepatitis B surface antigen (HBsAg), and negative anti-hepatitis B core (HBc) or; hepatitis B virus (HBV) DNA < LLOQ in subjects with isolated positive anti-HBc (i.e., negative HBsAg and Anti hepatitis B surface [HBs]) 
Disease Activity
 
 ✔ Positive anti- HCV antibody (Ab) AND Plasma HCV RNA viral load ≥ 1000 IU/mL at Screening and for at least 6 months before Screening. ✔ Any HCV GT allowed, including HCV GT1-, 2-, 3-, 4-, 5-, and/or 6-infection. Mixed GT and indeterminate GT may be acceptable. ✔ APRI SCORE ≤ 1, at time of Screening.

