5 STUDY ACTIVITIES

5.1 Eligibility Criteria

Subjects must meet all of the following criteria in order to be included in the study. Anything other than a positive response to the statements below will result in exclusion from study participation.

Consent

- ✓ 1. Subjects must voluntarily sign and date an informed consent, approved by an Independent Ethics Committee (IEC)/Institutional Review Board (IRB), prior to the initiation of any screening or study-specific procedures.

Demographic and Laboratory Assessments

- ✓ 2. Adult male or female, at least 18 years old at the time of screening.
- ✓ 3. Laboratory values meeting the following criteria within the Screening period prior to the first dose of study drug:
 - Platelets $\geq 150,000$ cells/mm³
 - ALT $\leq 10 \times$ ULN
 - AST $\leq 10 \times$ ULN
 - Direct bilirubin \leq ULN
 - Albumin \geq LLN
 - Calculated creatinine clearance (using Cockcroft-Gault method) ≥ 30 mL/min
 - A negative HBsAg, and negative anti-HBc or; HBV DNA $<$ LLOQ in subjects with isolated positive anti-HBc (i.e., negative HBsAg and Anti HBs)

Disease Activity

- ✓ 4. Positive anti-HCV Ab AND Plasma HCV RNA viral load ≥ 1000 IU/mL at Screening and for at least 6 months before Screening.
- ✓ 5. Any HCV GT allowed, including HCV GT1-, 2-, 3-, 4-, 5-, and/or 6-infection. Mixed GT and indeterminate GT may be acceptable.
- ✓ 6. APRI SCORE ≤ 1 , at time of Screening.

Medical History

- ✓ 7. No history of HCC.
- ✓ 8. No evidence of cirrhosis described as:
 - previous histologic diagnosis of cirrhosis on liver biopsy, e.g., METAVIR, Batts-Ludwig, Knodell, IASL, Scheuer, or Laennec fibrosis score of > 3 , Ishak score of > 4 in any liver biopsy conducted prior to Screening, OR
 - Any previous transient elastography score of ≥ 12.5 kPa, OR
 - Any current or historical clinical evidence of cirrhosis or decompensated cirrhosis, including any current or past evidence of Child-Pugh B or C classification, hepatic encephalopathy or variceal bleeding; radiographic evidence of ascites; or use of lactulose and/or rifaximin for hepatic encephalopathy prophylaxis or treatment.
- ✓ 9. Subject is treatment-naïve, e.g., has never received any other investigational or commercially available anti-HCV agents (e.g., interferon, peginterferon, RBV, telaprevir, boceprevir, simeprevir, asunaprevir, paritaprevir, grazoprevir, daclatasvir, ledipasvir, ombitasvir, elbasvir, dasabuvir, voxilaprevir or any other anti-HCV agent that is approved during the study).

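### Should the fixed 92.4% and 91.4% SVR12 thresholds be re-weighted if fewer than 20% of subjects have GT3?

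*Protocol*

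**What the plan says.** Protocol 7.3 defines efficacy against a historical control: "a threshold is determined by subtracting a non-inferiority margin of 6% from the historical" SVR12 rate. The mITT historical rates are "approximately 98.9% and 96.2" percent for non-GT3 and GT3, combined as a "weighted average of 80% GT1, GT2, GT4, GT5, and GT6 historical rate and 20% GT3 historical rate". The result is stated as 98.4%, hence 92.4%. For ITT, 1 point is taken off for non-virologic failure, giving 97.4% and then 91.4%. SAP 4.4 repeats this.

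The Synopsis describes the GT3 limit as a "maximum of 20% [46] enrollment of GT3 subjects". Protocol 7.3 and SAP 4.2.1 and 4.4 also treat it as a maximum. No minimum is given for any genotype, and Protocol 5.1 adds that "Mixed GT and indeterminate GT may be acceptable".

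SAP 6.2 and 6.3 compare the pooled SVR12 rate with the fixed thresholds. Neither document recalculates a threshold for the enrolled mix. SAP 5.2 tabulates genotype at baseline, and SAP 6.5 presents SVR12 in ITT and mITT by "HCV genotype (1, 2, 3, 4, 5, or 6) and available subtype".

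**The concern.** The weight sits at the enrolment ceiling. Apart from a small overshoot of an approximate cap, the GT3 share can only fall below 20%. GT3 has the lower historical rate, so on the plan's two rates a lower share raises the like-for-like control and makes a fixed threshold more lenient than the stated 6 points. By weighting on genotype, the plan itself accepts that the mix matters to the comparator.

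At stake is whether the primary claim of being within 6 points of historical control means what it says, and whether one subject near the boundary could decide it. A correction devised after results are known would carry little weight, so the question belongs at the planning stage.

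**Working it through.** **Inputs.** Historical rates 98.9% and 96.2%, margin 6 points, thresholds 92.4% and 91.4%, N about 230, 1% non-virologic failure (Protocol 7.3). Interval: two-sided 95% normal approximation, Wilson if there are fewer than five failures (Protocol 7.3, SAP 6.2). Study counts: Protocol 2.1. The enrolled GT3 share is not in the documents; 15%, 10% and 0% are illustrations.

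**1. The plan's figure.** With GT3 share w, H(w) = 98.9 − 2.7w. At w = 0.20, H = 98.36, which rounds to 98.4, and 98.4 − 6 = 92.4. Reproduced.

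**2. Implied margin, H(w) − 92.4.**

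| GT3 share | H(w) | Implied margin | Threshold for exactly 6 points |
|---|---|---|---|
| 20% | 98.36 | 5.96 | 92.36 |
| 15% | 98.495 | 6.10 | 92.495 |
| 10% | 98.63 | 6.23 | 92.63 |
| 0% | 98.90 | 6.50 | 92.90 |

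The ITT margins are the same, since both the rate and the threshold drop by 1 point.

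**3. Effect on the pass mark at N = 230 in mITT.** The lower bound is p − 1.96 × √(p(1 − p)/N). Eleven failures give 92.46% and ten give 93.02%, so the fixed threshold allows 11. The matched threshold is 92.454% at 38 GT3 subjects (11 still pass) and 92.466% at 37 (11 fail, 10 pass). It stays at 10 down to no GT3 subjects. In ITT at N = 230 the limit is 12 failures throughout.

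**4. Effect at the mITT size the plan implies.** The mITT set drops subjects who miss SVR12 "for reasons other than virologic failure". With 1% of 230 (2.3 subjects) removed, about 228 remain; with the observed 1.2%, about 227. Most failures allowed under the planned interval:

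| N in mITT | Fixed 92.4% | Matched, 15% GT3 | Matched, 10% GT3 | Matched, 0% GT3 |
|---|---|---|---|---|
| 218–226 | 10 | 10 | 10 | 9 |
| 227–228 | 10 | 10 | 10 | 10 |
| 229–231 | 11 | 10 | 10 | 10 |
| 232–235 | 11 | 11 | 10 | 10 |

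At N = 228, ten failures give 92.96%, above every matched threshold, and eleven give 92.39%, below the fixed one.

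**5. Pass probability if true SVR12 is exactly 6 points below the matched control (mITT, binomial).** At N = 230 the fixed threshold gives 5.9% at 20% GT3, 6.8% at 15% and 7.8% at 10%; matching lowers the last two to 3.8% and 4.4%. At N = 228 fixed and matched agree: 4.1% at 15% and 4.8% at 10%. The baseline above 2.5% comes from the normal-approximation interval, not the mix. With Wilson limits, the planned sensitivity analysis, the fixed-threshold figures at N = 230 are 1.6%, 1.9% and 2.3%.

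**6. Is matching on GT3 enough?** Taking missing-data subjects out of the denominators in Protocol 2.1: GT1 348/350 = 99.4%; GT2, 4, 5 and 6 196/200 = 98.0%; pooled 544/550 = 98.9%, the plan's figure. GT1 is therefore 350/550 = 64% of that pool. At 15% GT3, with GT1 share s among non-GT3 subjects, the threshold for exactly 6 points is 0.85 × (99.43s + 98.0(1 − s)) + 0.15 × 96.2 − 6:

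- s = 50%: 92.34%
- s = 64%: 92.50%
- s = 80%: 92.70%

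It equals 92.4% at s of about 55%. Below that, the existing threshold is already stricter than 6 points.

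**7. Precision of the historical rate.** Using 544/550 and 149/155 (96.1%, against the plan's approximate 96.2%), the standard error of the 80/20 rate is √(0.64 × 0.9891 × 0.0109/550 + 0.04 × 0.9613 × 0.0387/155) = 0.47 points, or ±0.9 points at 95%. The drift of 0.1 to 0.2 points is well inside that.

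**The case for a change.** The best case for a change is that it is cheap and looks safe. One formula, driven by baseline genotype among dosed subjects, would hold the margin at 6 points on the plan's two rates. It needs no new data and no outcome information, and it could be floored so the threshold never loosens. Power would stay high: under the plan's 98%/94% assumptions, planned-rule mITT power at N = 230 falls from 98.3% to 96.2% at 15% GT3 and from 99.0% to 97.6% at 10%. Disclosing the weights does not keep the margin at 6 points when the mix differs, and at N = 230 one subject could decide the primary endpoint.

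The arithmetic stands, and so does the point that the 6-point label is exact only near 20% GT3. The rest is weaker. The one-subject effect depends on where N falls relative to the steps of a discrete rule, and at the plan's expected mITT size it is absent. A formula in GT3 share alone would still leave the GT1 share unmatched, so it could overcorrect. It would also need a rounding rule, a floor and a convention for mixed or indeterminate genotypes. In an open-label single-arm trial, results accrue in view, so a threshold rewritten before database lock gains less credibility than one fixed in the protocol. The softer request, to report the enrolled GT3 share, is already met by SAP 5.2.

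**Conclusion.** No change is needed. On the plan's own rates the fixed thresholds imply a margin of about 6.1 points at 15% GT3 and 6.2 at 10%, with a ceiling of 6.5 if no GT3 subject enrols. At 15% GT3 the mITT pass mark moves by one failure only at N = 229 to 231 within the 218 to 235 range checked; at 227 or 228 it does not move at any GT3 share. The net direction of any leniency is not established once the GT1 share is considered, and the drift is smaller than the sampling error of the historical rate.

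This rests on three assumptions: illustrative GT3 shares, non-virologic failure near the plan's 1%, and the missing-data subjects in Protocol 2.1 being the only ones excluded from the historical mITT denominators. Keeping a simple, disclosed threshold is a fair trade-off. With the baseline genotype table, SVR12 by genotype and the overall confidence interval, a reader can work out the implied margin at the enrolled mix, and the study report could state it in a sentence without amending the plan.
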